For the purposes of this study, a female born subject is considered of childbearing potential following menarche until becoming post-menopausal, unless permanently sterile or with medically documented ovarian failure.

Women are considered to be in a postmenopausal state when they are ≥ 54 years of age with cessation of previously occurring menses for ≥ 12 months without an alternative cause.

Permanent sterilization includes hysterectomy, bilateral oophorectomy, or bilateral salpingectomy in a female subject of any age.

b. Definition of Male Fertility

For the purposes of this study, a male born subject is considered fertile after the initiation of puberty unless permanently sterile by bilateral orchidectomy or medical documentation.

2) Contraception Requirements for Female Subjects

a. Study Drug Effects on Pregnancy and Hormonal Contraception

Data from clinical pharmacokinetic interaction studies of SOF have demonstrated that there is no reduction in the clinical efficacy of hormonal contraception. Non-clinical toxicity studies of SOF have demonstrated no adverse effect on fertility or embryo-fetal development.

Data from clinical pharmacokinetic interaction studies of LDV have demonstrated that there is no reduction in the clinical efficacy of hormonal contraception. Non-clinical toxicity studies of LDV have demonstrated no adverse effect on fertility or embryo-fetal development.

However, the risks of treatment with LDV/SOF during pregnancy in human have not been evaluated. Please refer to the latest version of the IB for additional information.

b. Contraceptive Requirements for Female Subjects of Childbearing Potential

The inclusion of female subjects of childbearing potential requires using at least an acceptable effective contraceptive measure. They must have a negative serum pregnancy test at Screening and a negative pregnancy test on the Baseline/Day 1 visit prior to randomization. A pregnancy test will be performed at the Post Treatment Week 4 visit. They must also agree to one of the following from Screening until 30 days of the last dose of LDV/SOF.

- Complete abstinence from intercourse of reproductive potential. Abstinence is acceptable method of contraception only when it is in line with the subject's preferred and usual lifestyle. Periodic abstinence (eg, calendar, ovulation, symptothermal, post-ovulation methods) and withdrawal are not acceptable methods of contraception.

Or

- Consistent and correct use of 1 of the following methods of birth control listed below:
 - Intrauterine device (IUD)
 - Intrauterine hormone-releasing system (IUS)
 - Tubal sterilization
 - bilateral tubal occlusion
 - Vasectomy in male partner
 - Barrier methods (one female barrier and one male barrier must be used in combination)
 - Female barriers: Diaphragm with spermicide or Cervical cap with spermicide
 - Male barriers: Male condom (with or without spermicide)
 - Hormonal methods
 - Implants of levonorgestrel
 - Injectable progesterone
 - Oral contraceptives (either combined or progesterone only)
 - Contraceptive vaginal ring
 - Transdermal contraceptive patch

Female subjects must also refrain from egg donation and in vitro fertilization during treatment and until at least 30 days after the last dose of LDV/SOF.

3) Contraceptive Requirements for Males Subjects

During the study, male subjects with female partners of childbearing potential should use condoms until 30 days after the last dose of LDV/SOF treatment when engaging in intercourse of reproductive potential. If their female partner is of childbearing potential (as defined above), their female partner must use 1 of the methods of birth control listed above from the date of Screening until 30 days after the last dose of study drug.

Male subjects must agree to refrain from sperm donation for at least 30 days after the last dose of study drug.

4) Procedures to be Followed in the Event of Pregnancy

Subjects should be instructed to notify the investigator if they (or their partner) become pregnant at any time during the study, or if they become pregnant within 30 days of last study drug dose. Subjects who become pregnant or who suspect that they are pregnant during the study must report the information to the investigator and discontinue study drug immediately. Subjects whose partner has become pregnant or suspects she is pregnant must report the information to the investigator.

Instructions for reporting pregnancy, partner pregnancy, and pregnancy outcome are outlined in Section [7.6.2.1](#).

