4.2. Inclusion Criteria

Subjects must meet all of the following inclusion criteria to be eligible for participation in this study.

- 1) Parent or legal guardian must be able to provide written informed consent prior to any screening evaluations and willing to comply with study requirements. A subject will provide assent if possible; written assent will be provided if the subject has the ability to read and write, as determined by the Ethics Committee and the Investigator's assessment.
- 2) Male or female, 12 to <18 years of age (consent of parent or legal guardian required)
- 3) Weight \geq 35 kg
- 4) Chronic HCV infection (\geq 6 months) documented by medical history or, if available, liver biopsy
- 5) HCV genotype 1 or 4 at screening
- 6) Receiving a protocol-approved maintenance chemotherapy regimen for a hematological malignancy (see Section 5.3.1)
- 7) HCV RNA \geq 1000 IU/mL at screening
- 8) Adequate hematologic function (absolute neutrophil count \geq 500/mm³, hemoglobin \geq 10 g/dL)
- 9) Treatment naïve or experienced, where treatment-experienced is defined as prior treatment failure or intolerance to a regimen including interferon with or without ribavirin that was completed at least 8 weeks prior to Baseline/Day 1
- 10) Females of childbearing potential (as defined in Appendix 4) must have a negative pregnancy test at Screening and Baseline/Day 1.
- 11) Subject able to provide written assent, if they have the ability to read and write, as determined by IRB/IEC/local requirements and Investigator's discretion

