4.3. Exclusion Criteria

Subjects who meet *any* of the following exclusion criteria are not to be enrolled in this study.

- 1) Co-infection with HIV, acute hepatitis A virus (HAV) infection or chronic HBV coinfection (HBsAg positive [HBsAg+] at screening)
- 2) Decompensated liver disease defined as INR > 1.2 x ULN, platelets < 50,000/mm³, serum albumin < 3.0 g/dL, or prior history of clinical hepatic decompensation (eg, ascites, jaundice, encephalopathy, variceal hemorrhage)
- 3) Evidence of a gastrointestinal malabsorption syndrome that may interfere with absorption of orally administered medications
- 4) Chronic liver disease of non-HCV etiology (eg, hemochromatosis, Wilson's disease, alpha-1 antitrypsin deficiency)
- 5) Evidence of hepatocellular carcinoma (HCC) or other non-hematologic malignancy (with the exception of certain resolved skin cancers)

Note: liver imaging within 6 months of baseline/Day 1 is required in patients with cirrhosis to exclude HCC

- 6) History of solid organ or bone marrow transplantation
- 7) Active or recent history (\leq 1 year) of alcohol or drug abuse
- 8) Serum creatinine > 1.5 mg/dL
- 9) Estimated glomerular filtration rate < 90 mL/min/1.73m², as calculated by the Schwartz formula
- 10) Investigational agents taken within the past 28 days (except with the prior written approval of the Sponsor)
- 11) Use of any prohibited concomitant medications as described in Section 5.3
- 12) Pregnant or lactating subjects
- 13) Sexually-active males or females of childbearing potential who are not willing to use an effective method of contraception during the study (see [Appendix 4](#) for further details)
- 14) Unable to swallow the LDV/SOF FDC 90mg/400mg and the LDV/SOF FDC 22.5mg/100mg placebo tablets
- 15) Known hypersensitivity to LDV, SOF, metabolites, or formulation excipients
- 16) Subject unable to comply with the dosing instructions for study drug administration and/or unable to complete the study schedule of assessments

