6.7. Procedures and Specifications

6.7.1. Clinical Laboratory Analytes

- Hematology: Hematocrit, hemoglobin (Hb), platelet count, red blood cell count (RBC), white blood cell count (WBC) with differential (absolute and percentage) including lymphocytes, monocytes, neutrophils, eosinophils, basophils, reticulocyte count and MCV.
- Coagulation: INR, prothrombin time (PT), activated partial thromboplastin time (APTT).
- Chemistry: Alanine aminotransferase (ALT/SGPT), aspartate aminotransferase (AST/SGOT), albumin, alkaline phosphatase, creatinine, total bilirubin (reflex to direct bilirubin), glucose (non-fasting), potassium, sodium; gamma-glutamyl transferase (GGT)
- Fibrotest
- APRI
- Virological Tests: Serologies for HCV, HBV (HBsAg, HBsAb, HBcAb), HAV, and HIV. HCV RNA will be measured using the COBAS® AmpliPrep/COBAS® TaqMan® HCV Quantitative Test, version 2.0. HCV genotype and subtype will be determined using the Siemens VERSANT® HCV Genotype INNO-LiPA 2.0 Assay. HBV DNA testing will be performed only in subjects HBcAb positive at Screening. Alternate assays may be used if the above assays are not available or are not definitive.

- IL28B genotype will be determined by polymerase chain reaction (PCR) amplification of the SNP, rs12979860. Alternate assays may be used if this assay is not available.
- Pregnancy Tests: Serum β -hCG or urine β -hCG (if positive, requires immediate confirmation with serum β -hCG).

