Appendix 3. GSI Grading Scale for Severity of Adverse Events and Laboratory Abnormalities

Antiviral Toxicity Grading Scale Version: 25 August 2015 modified for Pediatric Studies

HEMATOLOGY				
	Grade 1	Grade 2	Grade 3	Grade 4
Hemoglobin HIV POSITIVE Adult and Pediatric ≥ 57 Days	8.5 to 10.0 g/dL 85 to 100 g/L	7.5 to < 8.5 g/dL 75 to < 85 g/L	6.5 to < 7.5 g/dL 65 to < 75 g/L	< 6.5 g/dL < 65 g/L
HIV NEGATIVE Adult and Pediatric ≥ 57 Days	10.0 to 10.9 g/dL 100 to 109 g/L OR Any decrease from Baseline 2.5 to < 3.5 g/dL 25 to < 35 g/L	9.0 to < 10.0 g/dL 90 to < 100 g/L OR Any decrease from Baseline 3.5 to < 4.5 g/dL 35 to < 45 g/L	7.0 to < 9.0 g/dL 70 to < 90 g/L OR Any decrease from Baseline ≥ 4.5 g/dL ≥ 45 g/L	< 7.0 g/dL < 70 g/L
Infant, 36–56 Days (HIV POSITIVE OR NEGATIVE)	8.5 to 9.4 g/dL 85 to 94 g/L	7.0 to < 8.5 g/dL 70 to < 85 g/L	6.0 to < 7.0 g/dL 60 to < 70 g/L	< 6.0 g/dL < 60 g/L
Infant, 22–35 Days (HIV POSITIVE OR NEGATIVE)	9.5 to 10.5 g/dL 95 to 105 g/L	8.0 to < 9.5 g/dL 80 to < 95 g/L	7.0 to < 8.0 g/dL 70 to < 80 g/L	< 7.0 g/dL < 70 g/L
Infant, 1–21 Days (HIV POSITIVE OR NEGATIVE)	12.0 to 13.0 g/dL 120 to 130 g/L	10.0 to < 12.0 g/dL 100 to < 120 g/L	9.0 to < 10.0 g/dL 90 to < 100 g/L	< 9.0 g/dL < 90 g/L
Absolute Neutrophil Count (ANC) Adult and Pediatric, ≥ 7 Months#	1000 to 1300/mm ³ 1.00 to 1.30 GI/L	750 to < 1000/mm ³ 0.75 to < 1.00 GI/L	500 to < 750/mm ³ 0.50 to < 0.75 GI/L	< 500/mm ³ < 0.50 GI/L

HEMATOLOGY				
	Grade 1	Grade 2	Grade 3	Grade 4
Absolute CD4+ Count HIV NEGATIVE ONLY Adult and Pediatric > 13 Years	300 to 400/mm ³ 300 to 400/μL	200 to < 300/mm ³ 200 to < 300/μL	100 to < 200/mm ³ 100 to < 200/μL	< 100/mm ³ < 100/μL
Absolute Lymphocyte Count HIV NEGATIVE ONLY Adult and Pediatric > 13 Years	600 to 650/mm ³ 0.60 to 0.65 GI/L	500 to < 600/mm ³ 0.50 to < 0.60 GI/L	350 to < 500/mm ³ 0.35 to < 0.50 GI/L	< 350/mm ³ < 0.35 GI/L
Platelets	100,000 to < 125,000/mm ³ 100 to < 125 GI/L	50,000 to < 100,000/mm ³ 50 to < 100 GI/L	25,000 to < 50,000/mm ³ 25 to < 50 GI/L	< 25,000/mm ³ < 25 GI/L
WBCs	2000/mm ³ to 2500/mm ³ 2.00 GI/L to 2.50 GI/L	1,500 to < 2,000/mm ³ 1.50 to < 2.00 GI/L	1000 to < 1,500/mm ³ 1.00 to < 1.50 GI/L	< 1000/mm ³ < 1.00 GI/L
Hypofibrinogenemia	100 to 200 mg/dL 1.00 to 2.00 g/L	75 to < 100 mg/dL 0.75 to < 1.00 g/L	50 to < 75 mg/dL 0.50 to < 0.75 g/L	< 50 mg/dL < 0.50 g/L
Hyperfibrinogenemia	> ULN to 600 mg/dL > ULN to 6.0 g/L	> 600 mg/dL > 6.0 g/L	— —	— —

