7.2.3. Graded Laboratory Values

The Gilead Grading Scale for Severity of Adverse Events and Laboratory Abnormalities will be used for assigning toxicity grades (0 to 4) to laboratory results for analysis. Grade 0 includes all values that do not meet the criteria for an abnormality of at least Grade 1. Some laboratory tests have criteria for both increased and decreased levels; analyses for each direction (ie, increased, decreased) will be presented separately.

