7.2.3.2. Summaries of Laboratory Abnormalities

Laboratory data that are categorical will be summarized using the number and percentage of subjects in the study with the given response at baseline and each scheduled postbaseline visit.

The following summaries (number and percentage of subjects) for treatment-emergent laboratory abnormalities will be provided by analyte and treatment group; subjects will be categorized according to the most severe postbaseline abnormality grade for a given analyte:

- Graded laboratory abnormalities
- Grade 3 or above laboratory abnormalities

For all summaries of laboratory abnormalities, the denominator is the number of subjects with nonmissing postbaseline values up to 30 days after last dose for the laboratory parameter of interest.

A by-subject listing of treatment-emergent Grade 3 or above laboratory abnormalities will be provided by subject ID number and visit in chronological order. This listing will include all test results that were collected throughout the study for the analyte of interest, with all applicable severity grades or abnormal flags displayed.

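### The only lymphocyte grading row starts above age 13 in a trial that enrols from 12, and the SAP keeps subjects it cannot grade in the denominator, so graded lymphocyte percentages can be understated

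*Protocol*

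**What the plan says.** Eligibility in Protocol 4.2 is "Male or female, 12 to <18 years of age". Protocol 4.3 excludes "Co-infection with HIV, acute hepatitis A virus (HAV) infection or chronic HBV coinfection", so the restriction of the lymphocyte row to HIV-negative subjects removes nobody, and age is the only limit that matters.

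Lymphocytes are measured: Protocol 6.7.1 lists "white blood cell count (WBC) with differential (absolute and percentage) including lymphocytes, monocytes, neutrophils". Protocol 8.6.3 defines graded abnormalities by Appendix 3, where the only lymphocyte row reads "Absolute Lymphocyte Count HIV NEGATIVE ONLY Adult and Pediatric > 13 Years". By contrast, the neutrophil row reads "Absolute Neutrophil Count (ANC) Adult and Pediatric, ≥ 7 Months", and the WBC and platelet rows carry no age limit.

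SAP 7.2.3 states that "Grade 0 includes all values that do not meet the criteria for an abnormality of at least Grade 1". SAP 7.2.3.1 calls an abnormality treatment-emergent when the value rises by at least one grade from baseline. For the summaries in SAP 7.2.3.2, "the denominator is the number of subjects with nonmissing postbaseline values up to 30 days after last dose for the laboratory parameter of interest". Neither document gives a lymphocyte criterion for younger subjects, a category for results that cannot be graded, or a denominator restricted to those that can.

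**The concern.** An incidence should have the same people at risk in its numerator and denominator. Here a subject at or below the age limit contributes to the denominator through having a value, but has no criterion by which any value, however low, could count as an event. The subject is treated as observed and event-free when in fact the event was never assessed.

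At stake is the accuracy of two percentages (any graded, and Grade 3 or above, treatment-emergent lymphocyte abnormality) and the completeness of the Grade 3 or above listing. All subjects receive maintenance chemotherapy for a hematological malignancy, and safety is one of the primary objectives, so a reader will look at this row. With 19 subjects, each one who cannot be graded is 1/19 = 5.3% of the denominator.

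**Working it through.** The plan states no lymphopenia rate and no number of subjects aged 13 or under, so there is no figure of its own to reproduce. The check has two parts.

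**1. Following one subject through the rules.** Take a 12-year-old with a postbaseline lymphocyte count of 200/mm³. In a 15-year-old this is Grade 4 (below 350/mm³ in Appendix 3).
- Appendix 3: no row applies, so no Grade 1 to 4 criterion can be met.
- SAP 7.2.3: a value meeting no Grade 1 or higher criterion is Grade 0.
- SAP 7.2.3.1: a rise of one grade is impossible when every value is Grade 0. The rule for a missing baseline does not help, because it still needs an abnormality of at least Grade 1.
- SAP 7.2.3.2: the value is nonmissing, so the subject is in the denominator. The subject is not in the numerator, nor in the Grade 3 or above listing.

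**2. Size.** Inputs: N = 19 enrolled (SAP 1.3), all assumed to have a postbaseline lymphocyte value; k = subjects with no applicable criterion (not given); x = subjects with a graded event among the other N − k; p = the rate in gradable subjects (not given).
- Percentage under the SAP: x/N.
- Percentage among gradable subjects: x/(N − k).
- Ratio of the two: (N − k)/N, so the relative shortfall is k/N.
- If younger subjects would have the same rate p under a suitable criterion, p is the rate for everyone and the SAP reports p × (19 − k)/19.

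Values of k are illustrations. If ages were spread evenly over the six eligible years, exact age would leave one year ungradable (19/6 ≈ 3). Completed years, with the limit read as 14 and older, would leave two (19/3 ≈ 6).

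| k | Relative shortfall k/19 | p = 20% | p = 40% | p = 60% |
|---|---|---|---|---|
| 0 | 0% | 20.0% | 40.0% | 60.0% |
| 1 | 5.3% | 18.9% | 37.9% | 56.8% |
| 3 | 15.8% | 16.8% | 33.7% | 50.5% |
| 6 | 31.6% | 13.7% | 27.4% | 41.1% |

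In whole subjects (all counts assumed):
- k = 3, x = 6: 6/19 = 31.6% against 6/16 = 37.5%.
- k = 6, x = 5: 5/19 = 26.3% against 5/13 = 38.5%.
- k = 4, x = 2: 2/19 = 10.5% against 2/15 = 13.3%.

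**The case against.** The best defence is that SAP 7.2.3 describes values tested against criteria and is silent on values that have none, so a programmer could leave the grade blank. That is a possible reading, but it does not cure the problem: the denominator in SAP 7.2.3.2 depends on a nonmissing value, not a nonmissing grade, so the subject is still counted.

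A second defence is that little is hidden. This is largely right. SAP 7.2.1 summarises lymphocytes numerically at each visit, including the minimum and change from baseline, and plots the median and quartiles. SAP 7.2 flags listed values outside the reference range whatever their grade. WBC, neutrophils and platelets are graded at age 12. Only the graded lymphocyte summaries and the Grade 3 or above listing are touched.

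A reader might infer that a severe lymphopenia in a 12-year-old would be reported as normal. There is some basis: Protocol 8.3 and 8.6.3 equate Grade 0 with normal, though in the rule for a missing pretreatment value. But the flags and numeric summaries mean that the low value still appears, so the inference fits the graded tables and not the report as a whole.

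Third, the size is assumed. The effect is nil if nobody at or below the age limit was enrolled, and the 35 kg minimum weight may thin out the youngest. Event counts may be small, because only worsening from baseline is counted, in subjects already on chemotherapy. Even for 6/19 the exact 95% interval is 12.6% to 56.6%, which dwarfs the shift. All of this limits the importance of the point. It does not make the denominator right.

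Finally, the laboratory summaries are descriptive, and the primary safety endpoint in Protocol 8.1.4 (AEs leading to permanent discontinuation) is not affected. That stands.

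**Conclusion.** The point holds as a defect in a stated rule: the eligible ages, the grading row and the denominator do not fit together, and no other section repairs the mismatch. The treatment-emergent graded and Grade 3 or above lymphocyte percentages can be understated by a relative k/19. That assumes all 19 subjects have a postbaseline value and that rates are equal across ages. If the ungradable subjects would have had no events under a suitable criterion, the full-denominator percentage would be correct.

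It would go too far to say that lymphopenia is understated in this trial. The documents give neither k nor an event rate, and SAP 3.4 and 5.1 split age at 15, so the planned age categories would not reveal k. They also do not say whether the limit in the row refers to exact age or completed years, which decides where 13-year-olds fall. This is a minor point confined to one analyte, worth correcting because it is cheap to correct.

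**What to change.** In SAP 7.2.3, add that a result with no age-applicable criterion in Appendix 3 is classed as not gradable rather than Grade 0, and state whether the limit of 13 years is applied to exact age or to completed years at first dose. In SAP 7.2.3.2, restrict the lymphocyte denominator to subjects with an applicable criterion, and footnote the number excluded.

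Shrinking the denominator corrects the percentage for the gradable subjects but does not show what happened to the others. The same table should therefore report, for the excluded subjects, how many had a postbaseline lymphocyte value below the laboratory reference range. No new listing is needed, since SAP 7.2 already lists and flags these values.

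The cost is a few sentences, one programming flag and one extra count. The downside is a slightly smaller denominator for one analyte. SAP section 1 has the SAP finalised before database finalisation and later changes documented in the CSR, so the correction can be made by either route.

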4. SUBJECT POPULATION

4.1. Number of Subjects and Subject Selection

Approximately 40 treatment naïve or experienced pediatric subjects will be enrolled in this study. Male and female children 12 to < 18 years of age, with genotype 1 or 4 HCV infection, and who are receiving a maintenance cancer chemotherapy regimen will be enrolled.

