7.2.2. Assessment of Severity

Severity should be recorded and graded according to the Gilead Sciences, Inc. (GSI) Grading Scale for Severity of AEs and Laboratory Abnormalities (see [Appendix 3](#)). For AEs associated with laboratory abnormalities, the event should be graded on the basis of the clinical severity in the context of the underlying conditions; this may or may not be in agreement with the grading of the laboratory abnormality.

7.3. Investigator Requirements and Instructions for Reporting Adverse Events and Serious Adverse Events to Gilead

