7.5. Toxicity Management

7.5.1. Subject Stopping Rules

The Gilead Medical Monitor must be consulted prior to dose discontinuation of LDV/SOF FDC unless the investigator believes that immediate action is warranted to ensure the continued safety of the subject.

Due to a clinical or laboratory event, administration of study drug may be discontinued. If LDV/SOF FDC is stopped due to toxicity, it must not be restarted, and the subject must complete an ESDD visit. If possible, all subjects who terminate treatment early will complete the Early Study Drug Discontinuation (ESDD) Visit, and Post-Treatment Weeks 4, 12, and 24 Visits.

Subjects who meet any of the following laboratory criteria must stop study drug:

- Elevation of ALT and/or AST > 5x Day 1 or nadir, confirmed by immediate repeat testing
- Abnormal elevation of ALT > 3 x Day 1 and direct bilirubin > 2 x baseline, confirmed by immediate repeat testing.
- Elevation of ALT > 15 x ULN, confirmed by immediate repeat testing
- Any Grade 3 or greater rash associated with constitutional symptoms
- Any Grade 4 adverse event or laboratory abnormality assessed as related to LDV/SOF FDC

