ENZYMES				
	Grade 1	Grade 2	Grade 3	Grade 4
AST (SGOT)	1.25 to 2.50 × ULN	> 2.50 to 5.00 × ULN	> 5.00 to 10.00 × ULN	> 10.00 × ULN
ALT (SGPT)	1.25 to 2.50 × ULN	> 2.50 to 5.00 × ULN	> 5.00 to 10.00 × ULN	> 10.00 × ULN
GGT	1.25 to 2.50 × ULN	> 2.50 to 5.00 × ULN	> 5.00 to 10.00 × ULN	> 10.00 × ULN
Alkaline Phosphatase	1.25 to 2.50 × ULN	> 2.50 to 5.00 × ULN	> 5.00 to 10.00 × ULN	> 10.00 × ULN
Total Amylase	> 1.0 to 1.5 × ULN	> 1.5 to 2.0 × ULN	> 2.0 to 5.0 × ULN	> 5.0 × ULN
Pancreatic Amylase	> 1.0 to 1.5 × ULN	> 1.5 to 2.0 × ULN	> 2.0 to 5.0 × ULN	> 5.0 × ULN
Lipase	> 1.0 to 1.5 × ULN	> 1.5 to 3.0 × ULN	> 3.0 to 5.0 × ULN	> 5.0 × ULN
Albumin Pediatrics <16 years	-	2.0 to < LLN g/dL 20 to < LLN g/L	< 2.0 g/dL < 20 g/L	NA
≥ 16 years	3.0 g/dL to < LLN 30 g/L to < LLN	2.0 to < 3.0 g/dL 20 to < 30 g/L	< 2.0 g/dL < 20 g/L	NA

URINALYSIS				
	Grade 1	Grade 2	Grade 3	Grade 4
Hematuria (Dipstick)	1+	2+	3-4+	NA
Hematuria (Quantitative) See Note below				
Females	>ULN - 10 RBC/HPF	> 10-75 RBC/HPF	> 75 RBC/HPF	NA
Males	6-10 RBC/HPF	> 10-75 RBC/HPF	> 75 RBC/HPF	NA
Proteinuria (Dipstick)	1+	2-3+	4+	NA
Proteinuria, 24 Hour Collection				
Adult and Pediatric ≥ 10 Years	200 to 999 mg/24 h	>999 to 1999 mg/24 h	>1999 to 3500 mg/24 h	> 3500 mg/24 h
Pediatric > 3 Mo to < 10 Years	201 to 499 mg/m ² /24 h	>499 to 799 mg/m ² /24 h	>799 to 1000 mg/m ² /24 h	> 1000 mg/ m ² /24 h
Glycosuria (Dipstick)	1+	2-3+	4+	NA

Notes:

- Toxicity grades for Quantitative and Dipstick Hematuria will be assigned by Covance Laboratory, however for other laboratories, toxicity grades will only be assigned to Dipstick Hematuria.
- With the exception of lipid tests, any graded laboratory test with a result that is between the LLN and ULN should be assigned Grade 0.
- If the severity of a clinical AE could fall under either one of two grades (e.g., the severity of an AE could be either Grade 2 or Grade 3), select the higher of the two grades for the AE.

CARDIOVASCULAR				
	Grade 1	Grade 2	Grade 3	Grade 4
Cardiac Arrhythmia (general) (By ECG or physical exam)	Asymptomatic AND No intervention indicated	Asymptomatic AND Non-urgent medical intervention indicated	Symptomatic, non-life-threatening AND Non-urgent medical intervention indicated	Life-threatening arrhythmia OR Urgent intervention indicated
Cardiac-ischemia/Infarction	NA	NA	Symptomatic ischemia (stable angina) OR Testing consistent with ischemia	Unstable angina OR Acute myocardial infarction

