Hemorrhage (significant acute blood loss)	NA	Symptomatic AND No transfusion indicated	Symptomatic AND Transfusion of ≤ 2 units packed RBCs (for children ≤ 10 cc/kg) indicated	Life-threatening hypotension OR Transfusion of > 2 units packed RBCs indicated (for children ≤ 10 cc/kg) indicated
Hypertension (with repeat testing at same visit)	140–159 mmHg systolic OR 90–99 mmHg diastolic	> 159–179 mmHg systolic OR > 99–109 mmHg diastolic	> 179 mmHg systolic OR > 109 mmHg diastolic	Life-threatening consequences (eg, malignant hypertension) OR Hospitalization (other than ER visit) indicated
Pediatric ≤ 17 Years (with repeat testing at same visit)	NA	91st–94th percentile adjusted for age, height, and gender (systolic and/or diastolic)	≥ 95th percentile adjusted for age, height, and gender (systolic and/or diastolic)	Life-threatening consequences (eg, malignant hypertension) OR Hospitalization indicated (other than emergency room visit)
Hypotension	NA	Symptomatic, corrected with oral fluid replacement	Symptomatic, IV fluids indicated	Shock requiring use of vasopressors or mechanical assistance to maintain blood pressure
Pericardial Effusion	Asymptomatic, small effusion requiring no intervention	Asymptomatic, moderate or larger effusion requiring no intervention	Effusion with non-life-threatening physiologic consequences OR Effusion with nonurgent intervention indicated	Life-threatening consequences (eg, tamponade) OR Urgent intervention indicated

CARDIOVASCULAR				
	Grade 1	Grade 2	Grade 3	Grade 4
Prolonged PR Interval Pediatric ≤ 16 Years	PR interval 0.21 to 0.25 sec 1st degree AV block (PR > normal for age and rate)	PR interval > 0.25 sec Type I 2nd degree AV block	Type II 2nd degree AV block OR Ventricular pause > 3.0 sec Type II 2nd degree AV block	Complete AV block Complete AV block
Prolonged QTc Pediatric ≤ 16 Years	Asymptomatic, QTc interval 0.45 to 0.47 sec OR Increase interval < 0.03 sec above baseline	Asymptomatic, QTc interval 0.48 to 0.49 sec OR Increase in interval 0.03 to 0.05 sec above baseline	Asymptomatic, QTc interval ≥ 0.50 sec OR Increase in interval ≥ 0.06 sec above baseline	Life-threatening consequences, eg, Torsade de pointes or other associated serious ventricular dysrhythmia
	Asymptomatic, QTc interval 0.450 to 0.464 sec	Asymptomatic, QTc interval 0.465 to 0.479 sec	Asymptomatic, QTc interval ≥ 0.480 sec	Life-threatening consequences, eg, Torsade de pointes or other associated serious ventricular dysrhythmia

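### Appendix 3 prints the same transfusion limit for children (≤ 10 cc/kg) in the Grade 4 haemorrhage cell as in the Grade 3 cell, and Grade 4 feeds a mandatory stop (minor)

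*Protocol*

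**What the plan says.** Protocol Appendix 3 grades significant acute blood loss partly by the transfusion indicated. For Grade 3 the subject must be symptomatic, with "Transfusion of ≤ 2 units packed RBCs (for children ≤ 10 cc/kg) indicated". For Grade 4 there must be either life-threatening hypotension or "Transfusion of > 2 units packed RBCs indicated (for children ≤ 10 cc/kg) indicated". A note in the same appendix, below the urinalysis table, deals with a clinical event that could fall under either of two grades: "select the higher of the two grades for the AE".

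The limit for children is the one that matters here. Protocol 4.1 describes the population as "Male and female children 12 to < 18 years of age".

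The scale has a direct operational role. Protocol 7.2.2 states: "Severity should be recorded and graded according to the Gilead Sciences, Inc. (GSI) Grading Scale". Protocol 7.5.1 then lists, among the events that require study drug to stop, "Any Grade 4 adverse event or laboratory abnormality assessed as related to LDV/SOF FDC". It adds: "If LDV/SOF FDC is stopped due to toxicity, it must not be restarted".

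**The concern.** A severity scale has to separate adjacent grades. In this row the unit limits do so, because ≤ 2 units and > 2 units cannot both be true. The limits for children do not, because the same inequality appears in both cells. The limit relevant to every subject in the trial therefore fails to distinguish Grade 3 from Grade 4.

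What is at stake is the stopping rule. If a haemorrhage is judged related to LDV/SOF, Grade 4 makes the stop mandatory and permanent, whereas Grade 3 does not trigger that rule. Read literally, the cell could prompt a stop after a small transfusion and give no Grade 4 signal after a large one.

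**Working it through.** The plan states no figure on this point, so there is none to reproduce. The check is to apply the printed cells to a range of transfusion volumes.

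Inputs:
- Grade 3 limit for children: ≤ 10 cc/kg, in a symptomatic subject (Appendix 3, Hemorrhage).
- Grade 4 limit for children: ≤ 10 cc/kg as printed (same row).
- Tie-break: the higher grade is taken (Appendix 3, notes).
- Minimum weight at entry: 35 kg (Protocol 4.2, criterion 3).

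Take a symptomatic child without life-threatening hypotension and apply the limits for children. The last column replaces the Grade 4 limit by > 10 cc/kg, the mirror of Grade 3.

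| Transfusion indicated (cc/kg) | Meets Grade 3 as printed | Meets Grade 4 as printed | Grade after tie-break | Grade if the Grade 4 limit is > 10 |
|---|---|---|---|---|
| 2 | yes | yes | 4 | 3 |
| 5 | yes | yes | 4 | 3 |
| 10 | yes | yes | 4 | 3 |
| 10.1 | no | no | none | 4 |
| 15 | no | no | none | 4 |
| 20 | no | no | none | 4 |

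As printed, every volume up to and including 10 cc/kg falls in both cells, and every volume above it falls in neither. Grade 2 cannot absorb the larger volumes, because it requires that no transfusion be indicated. With the mirrored limit each volume has exactly one grade, so both the overlap and the gap disappear.

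In absolute terms the boundary is 10 cc/kg × body weight:
- 35 kg (entry minimum): 10 × 35 = 350 cc
- 50 kg (illustrative): 10 × 50 = 500 cc
- 70 kg (illustrative): 10 × 70 = 700 cc

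The effect on reporting follows from the adverse event summaries listed in Protocol 8.6.2 and SAP 7.1.6. Their severity cut-offs are Grade 2 or above and Grade 3 or above. An event recorded as Grade 4 in place of Grade 3 is counted in both either way, so that swap changes no listed summary. It would show only in the by-subject listings.

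**The case against.** The strongest reply is that this is a slip with little consequence. The unit limits in the same row make the intended > 10 cc/kg evident, and an experienced investigator would probably grade accordingly. The stop applies only to a bleed judged related to LDV/SOF. Protocol 7.5.1 requires the Medical Monitor to be consulted before study drug is discontinued, unless immediate action is needed, so a literal misreading would normally meet sponsor review first. In the other direction, 7.5.1 and 3.6 let the investigator stop drug for toxicity without a Grade 4 label. All of this stands, and it is why the point is minor.

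A second reply is that the point turns on one character, and inequality signs can change when a PDF table is read as text. That also stands as a caution. The repeated word at the end of the Grade 4 cell suggests a copying slip in the source, but it does not prove the sign, so the original page must be checked.

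A third reply is that re-checking grades may not be possible from the planned listings. Neither document says that transfusion volume is collected. Protocol 7.1.1 says a transfusion is not itself an adverse event, and the criterion concerns the transfusion indicated, not the volume given. This stands too, and the fix allows for site queries.

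None of these replies makes the printed cell correct. A threshold that feeds a mandatory stop should not depend on the reader noticing the error.

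**Conclusion.** Wrong as written, and minor. The Grade 4 limit for children repeats the Grade 3 limit. A symptomatic child with ≤ 10 cc/kg indicated is pushed up to Grade 4, and one above 10 cc/kg meets neither limit for children. The conclusion assumes that the printed sign is confirmed on the original page and that the limit for children applies to all subjects, as Protocol 4.1 implies. Nothing in the documents shows that any subject was wrongly stopped or wrongly continued, and no effect on SVR12 is claimed.

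Two stronger readings are tempting but not supported.

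- A reader might infer that larger transfusions actually receive the lower grade, because a child above 10 cc/kg but within 2 units would be Grade 3. That requires the unit limits to apply to children as well, although the bracketed limit more naturally replaces them. It also requires a unit volume that the documents do not give.
- A reader might infer a related gap in the liver stop in Protocol 7.5.1, "Abnormal elevation of ALT > 3 x Day 1 and direct bilirubin > 2 x baseline, confirmed by immediate repeat testing", because Protocol 6.7.1 lists direct bilirubin only as a reflex from total bilirubin. No trigger is stated, but it may be in the study procedures manual cited in Protocol 6, and nothing shows a missing baseline. Direct bilirubin also cannot exceed total, so an on-treatment direct value above twice baseline total bilirubin already meets the bilirubin condition. No defect is established there.

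**What to change.** First, confirm the sign in the Grade 4 haemorrhage cell on the original page of Appendix 3. If it is as printed, change the Grade 4 limit for children to > 10 cc/kg, with agreement from the sponsor's clinical team. This is one symbol, although Protocol 9.2.1 requires IRB or IEC approval of any protocol modification. SAP 1.3 says enrolment ended at 19 subjects and SAP 3.2 describes dosing in the past tense. The text change is therefore unlikely to alter a stop in this trial; it mainly corrects the scale in case it is reused.

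Second, before database finalization, find any haemorrhage event among the 19 subjects in the all-AE listing planned in SAP 7.1.6 and compare its grade with the corrected cell. Where the indicated transfusion volume is not recorded, send a site query. Grades belong to the investigator (SAP 7.1.2), so any change should come through that query. Report any affected case in the CSR. The cost is one pass through a listing for 19 subjects, plus a query for each haemorrhage whose indicated volume is missing; the number of such events cannot be derived from the documents.
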